### 7.2.5. Visit 4 (Up to and including 3 days prior to surgical resection)

The following assessments and procedures will be performed:

**NB: if surgery is delayed by > 7 days, all visit 4 assessments should be repeated up to and including 3 days before the rescheduled surgery.**

- Physical examination will be conducted, as described in section 7.3.4
- Vital signs will be taken, as described in section 7.3.5
- Performance status will be assessed, as described in section 7.3.6
- Record any concomitant medications, as described in section 7.3.20
- Record any adverse events, as described in section 7.3.21
- Blood samples for biochemistry, haematology and coagulation, as described in section 7.3.8
- A 12-lead ECG will be taken, as described in section 7.3.12
- Liver MRI, incorporating DCE-MRI, as described in section 7.3.11
- CT scan of chest, abdomen & pelvis, incorporating perfusion CT of liver, as described in section 7.3.11.
- Blood sample for biomarkers, as described in section 7.3.13
- Blood sample for serum tumour markers, as described in section 7.3.10
- Blood sample for vandetanib and metabolite analysis, as described in section 7.3.14

### 7.2.6. Visit 5 Surgical Resection (7 to 21 days following treatment with BTG-002814)

The following assessments and procedures will be performed:

- Vital signs will be taken before surgery, as described in section 7.3.5
- Record any concomitant medications, as described in section 7.3.20
- Record any adverse events, as described in section 7.3.21
- Samples of resected liver will be taken for vandetanib and metabolite analysis, as described in section 7.3.15 and for histopathological and biomarker analysis as described in section 7.3.16

### 7.2.7. Visit 6 End of Study/Early Withdrawal (28-32 days postsurgery)

Patients complete the study 28-32 days following the day of surgical resection. The following assessments and procedures will be performed for those patients who complete the study or those who withdraw early.

- Physical examination will be conducted, as described in section 7.3.4
- Vital signs will be taken, as described in section 7.3.5
- Performance status will be assessed, as described in section 7.3.6
- Record any concomitant medications, as described in section 7.3.20

- 
- 

- Record any adverse events, as described in section 7.3.21. Any AEs related to BTG-002814 continuing at this visit should be recorded as 'ongoing' in the patient's medical notes and CRFs.
- Blood samples for biochemistry, haematology and coagulation, as described in section 7.3.8
  - A 12-lead ECG will be taken, as described in section 7.3.12
  - Blood sample for biomarkers, as described in section 7.3.13
  - Blood sample for vandetanib and metabolite analysis, as described in section 7.3.14
- As appropriate, record the date and reason for study completion as listed in section 5.4 □  
As appropriate, record the date and reason for study withdrawal as listed in section 5.5

## 7.3. Study Evaluations and Procedures

### 7.3.1. Informed Consent Process

Sites are responsible for assessing a patient's capacity to give informed consent.

Sites must assess a patient's ability to understand verbal and written information in English and whether or not an interpreter would be required to ensure fully informed consent. If a patient requires an interpreter and none is available, the patient should not be considered for the study.

Patients with the potential to meet eligibility criteria may be offered the opportunity to be evaluated for participation in this clinical study. All such patients must sign the current REC approved informed consent form (ICF) before any study-related evaluations can be performed.

The Investigator or delegate will review the study and the treatment plan with the patients and the patients will have an opportunity to ask questions about study procedures, the required visit schedule, risks and benefits of the study treatment and alternative treatment options prior to signature of the ICF. The patient will receive a copy of the signed ICF to keep for their records.

A **minimum of twenty four (24) hours** must be allowed for the patient to consider and discuss participation in the study.

The discussion and consent process must be documented in the patient notes.

Site staff are responsible for:

- checking that the current REC-approved version of the patient information sheet and consent form are used
- checking that information on the consent form is complete and legible
- checking that the patient has completed/initialled all relevant sections and signed and dated the form
- checking that an appropriate member of staff has countersigned and dated the consent form to confirm that they provided information to the patient
- checking that an appropriate member of staff has made dated entries in the patient's medical notes relating to the informed consent process (i.e., information given, consent signed etc.)
- following registration, adding the patients' study number to all copies of the consent form, which should be filed in the patient's medical notes and Investigator Site File
- giving the patient a copy of their signed consent form, patient information sheet and patient contact card

- 
- 

Patients will be informed of any revisions to the ICF and any revisions must be signed and kept in the patient study file.

Each time an ICF is administered (original and subsequent revisions as appropriate), the process of obtaining the patient's informed consent should be documented in the patient's medical record and the ICF signed and dated by the individual who conducted the informed consent discussion.

The right of the patient to refuse to participate in the study without giving reasons must be respected. All patients are free to withdraw at any time.

### 7.3.2. Demographics

The following demographic data will be obtained: date of birth/age, gender, child-bearing potential, race and ethnicity.

### 7.3.3. Medical History

Medical history deemed clinically significant by the Investigator will be collected per body system. Diagnosis and medical history for HCC and mCRC will be recorded separately from other medical history.

All ongoing medical conditions and AEs arising from treatment of those conditions present for 30 days or more prior to entering the study are generally considered a part of the patient's medical history and must be recorded at Screening.

### 7.3.4. Physical Examination

A full physical examination, including height (required at Screening only) and weight, will be performed by a qualified licensed individual. A review of body systems will include the following:

- General appearance
- Skin
- Head, Ears, Eyes, Nose, Throat
- Respiratory
- Cardiovascular
- Abdomen (including liver and kidneys)
- Musculoskeletal □ Neurological

Any abnormalities or changes in intensity noted during the initial review of body systems should be documented in the patient's medical notes and CRFs. If a new clinically significant finding (i.e., not noted at Screening) or change in intensity occurs at subsequent visits, this must be documented as an AE. Resolution of any abnormal findings during the study will be noted in the patient's medical notes and CRFs.

### 7.3.5. Vital Signs

Assessments of vital signs (i.e., BP and HR) will be performed at all study visits. When possible, BP and HR will be determined after the patient has been in the sitting position for 5 minutes.

Any clinically significant changes from Screening will be recorded as an AE.

### 7.3.6. Performance Status

WHO performance status will be assessed according to the following categories:

Grade	WHO Description
0	Fully active, able to carry on all pre-disease performance without restriction
1	Restricted in physically strenuous activity but ambulatory and able to carry out work of a light or sedentary nature, e.g., light house work, office work

2	Ambulatory and capable of all selfcare but unable to carry out any work activities. Up and about more than 50% of waking hours
3	Capable of only limited selfcare, confined to bed or chair more than 50% of waking hours
4	Completely disabled. Cannot carry on any selfcare. Totally confined to bed or chair
5	Dead

### 7.3.7. Medication and Prior Treatment History

The use of concurrent medications (medications taken within 30 days of Screening and during the conduct of the study) will be obtained and documented in the patient's medical notes and CRFs.

Prior treatment history for HCC and mCRC will also be recorded.

### 7.3.8. Clinical Laboratory Evaluations – Biochemistry, Coagulation Parameters, Haematology

All clinical laboratory tests will be performed at the local laboratory according to the laboratory's normal procedures. Reference ranges will be supplied by the laboratory and used to assess the laboratory data for clinical significance and out-of-range pathological changes. The Investigator should assess out-of-range laboratory values for clinical significance, indicating if the value(s) is/are not clinically significant or clinically significant. Abnormal laboratory values, which are unexpected or not explained by the patient's clinical condition, should be repeated until confirmed, explained or resolved. Repeat evaluations should be performed as soon as possible after the original evaluation.

Changes from Screening will be recorded as an AE if assessed as clinically significant by the Investigator.

The following clinical laboratory assessments will be completed as per the Schedule of Visits:

#### Biochemistry

Blood samples for biochemistry will be taken.

- Sodium
- Potassium
- Calcium
- Magnesium
- Urea
- Creatinine
- Albumin
- Total Protein
- Alanine transaminase (ALT)
- Aspartate transaminase (AST), if ALT not available
- Alkaline phosphatase (ALP)
- Gamma glutamyl transferase (GGT)

- Total bilirubin
- Random glucose
- Lactate Dehydrogenase (LDH)
- Urate
- Thyroid Stimulating Hormone (TSH)
- Calculated GFR (using a validated creatinine clearance calculation)

### **Coagulation Parameters**

Blood samples for coagulation parameters will be taken.

- Prothrombin Time (PT)
- Partial Thromboplastin Time (PTT)
- International Normalised Ratio (INR)

### **Haematology**

Blood samples for haematology will be taken.

- Haemoglobin
- Haematocrit
- White Blood Cell (WBC) Count
- Platelet Count
- WBC- differential and Absolute Neutrophil Count (ANC)
- Red Blood Cell (RBC) Count □ Mean corpuscular volume (MCV)

### **7.3.9. Pregnancy Test**

All WOCBP will have a serum beta hCG pregnancy test at the Screening Visit to assess their suitability for entry into the study.

### **7.3.10. Serum Tumour Markers**

The following clinical laboratory tests will be performed at the local laboratory according to the laboratory's normal procedures. Reference ranges will be supplied by the laboratory and used to assess the laboratory data for clinical significance and out-of-range pathological changes.

The following clinical laboratory assessments will be completed as per the Schedule of Visits:

Patients with HCC:

- serum alpha-fetoprotein (AFP) Patients with mCRC:
- serum CEA
- serum CA19-9
- serum CA125

### **7.3.11. Imaging including Dynamic Imaging**

Since measurement of perfusion characteristics may improve understanding of liver tumour biology and behaviour, patients in this study will undergo dynamic contrast enhanced (DCE) magnetic resonance imaging (MRI) and perfusion Computed Tomography (pCT) at timepoints stated in the Schema. pCT and DCE-MRI will be combined with routine scans and study visits where possible, although additional visits to the Radiology Department may be required.

## DCE-MRI

For DCE-MRI, patients will lie supine on the scanner table and an intravenous cannula placed in the antecubital fossa. No oral contrast is required. After acquisition of standard clinical MRI liver sequences, T1 mapping will be performed using three-dimensional volumetric gradient echo imaging with varying flip angles. A series of T1-weighted three-dimensional volumetric images will be acquired at baseline and at short intervals during administration of a bolus of intravenous paramagnetic MR contrast agent at a rate of 3-5 mL/s. Each acquisition takes approximately 5 seconds during which time patients are asked to hold their breath in full expiration or if necessary to breathe in a shallow fashion. The entire post contrast DCE series takes approximately 3-5 minutes.

Liver parenchyma and tumour signal intensity curves will be used to calculate semiquantitative and quantitative tissue parameters describing tumour perfusion, blood flow and vascularity, using a compartment model with an arterial and portal venous input function.

Assessment of changes in blood flow on DCE-MRI following treatment with BTG-002814.  $K^{trans}$ ,  $K^{ep}$  and  $V^e$  will be derived from DCE-MRI images.

## CT

CT will incorporate dual energy (DECT) and perfusion imaging (pCT) of the liver, in addition to standard clinical contrast enhanced imaging of the chest, abdomen and pelvis. CT should be performed before or at least 90 minutes after the MRI scan. Images will be acquired in a supine position using a cannula placed in the antecubital fossa, and no oral contrast is required. A combined CT protocol will be carried out as follows, with each volume acquired in inspiration:

1. dual energy (80+135 kV) acquisition of the liver prior to contrast administration
  2. bolus of 0.5 mL/kg of iodinated contrast (300 mgI/mL) injected at a rate of no less than 5 mL/s (total <8 seconds).
  3. volume perfusion acquisition of the liver, with intermittent scanning over 90 seconds
  4. interval of at least 3 minutes to allow contrast washout
  5. bolus of 1 mL/kg of iodinated contrast (300 mgI/mL) injected at a rate of 3-5 mL/s
  6. late arterial phase (35 seconds post contrast bolus) volume of the chest and liver
  7. portal venous phase (60 seconds post contrast bolus) volume of the abdomen and pelvis
- Data from CT and DCE-MRI will be used in developing the 3D modelling of the distribution of BTG-002814.

Following treatment with BTG-002814 a 4D CT scan will be performed to check and track the positioning of the beads in 'real time'. This scan should be performed without contrast.

### 7.3.12. ECG Assessment

A 12-lead ECG reading will be taken as per the Investigator's standard practice.

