Conventional TACE (cTACE) involves the administration of an anticancer agent followed by an embolic agent into the tumour feeding arteries to block its major nutrient source resulting in ischemic necrosis of the targeted tumour. The most common anticancer cytotoxic drugs for local delivery via TACE are doxorubicin, cisplatin, epirubicin, mitoxantrone and mitomycin C. However, the systemic release of chemotherapy agents following cTACE is high and many patients suffer from systemic side effects. These factors led to innovative research to develop a different method of local drug delivery with less of the systemic toxicity associated with cTACE. One of these methods is the use of drug-eluting microspheres for TACE, henceforth referred to as drug-eluting bead TACE (DEB-TACE) (Lewis et al., 2006; Poon et al., 2007; Varela et al., 2007).

DEB-TACE ensures slow and sustained release of the drug locally ensuring high intra-tumoural drug concentrations in addition to the ischaemic effects of the embolic agent. In vitro data have confirmed the slow, sustained release of the drug (Lewis et al., 2006) and it has been shown in HCC patients that TACE with drug-eluting microspheres (DC Bead™) achieves higher intratumoural concentrations and lower systemic concentrations of cytotoxic agent than cTACE, thereby reducing the potential liver toxicity of treatment (Poon et al., 2007; Varela et al., 2007).

TACE using drug-eluting beads loaded with doxorubicin (DEBDOX) has been widely performed in patients with HCC and has become the standard therapy for patients not suitable for surgical resection or transplantation (Lencioni, Petruzzi & Crocetti, 2013). Current international guidelines from the American Association for the Study of Liver Disease (AASLD) and the European Association for the Study of the Liver (EASL) recommend TACE as first-line, non-curative therapy for non-surgical patients with large/multifocal HCC who do not have vascular invasion or extrahepatic spread (Bruix, Sherman & American Association for the Study of Liver, 2011; EASL & EORTC, 2012).

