#### Post-treatment Assessments

The following assessments and procedures will be performed on the day of treatment after administration of BTG-002814:

- Vital signs will be taken, as described in section 7.3.5. Peak heart rate (HR) and peak blood pressure (BP) should be recorded in the CRF
- Record any concomitant medications, as described in section 7.3.20
- Record any adverse events, as described in section 7.3.21
- A 12-lead ECG will be taken, as described in section 7.3.12
- Blood samples for vandetanib and metabolite analysis at 2 and 4 hours after treatment, as described in section 7.3.14

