#### **Safety data with the use of oral vandetanib to treat medullary thyroid cancer**

Oral vandetanib is a standard therapy used to treat medullary thyroid cancer. Vandetanib produces repolarisation abnormalities in human myocardium that are consistent with blockade of the  $I_{KR}$  (potassium) channel. The most consistent electrophysiologic effects are a change in Twave morphology (flattening, broadening or notching) and prolongation of the QT interval, both of which occur more commonly as the dose is increased. Vandetanib can cause rash, diarrhoea and hypertension, all of which appear to be dose-related and are likely to be related to the pharmacologic activity of vandetanib.

For the full list of known Adverse Reactions and safety warnings, refer to the current version of the BTG-002814 IB.

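### The one post-treatment ECG on treatment day has no set time and no link to a plasma sample, so a null treatment-day QTc change cannot be told apart from little exposure yet

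*Protocol*

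**What the plan says.** **ECG.** Protocol 7.3.12 is a single sentence: "A 12-lead ECG reading will be taken as per the" investigator's usual practice. The post-treatment list for Visit 2 (Protocol 7.2.3) has one ECG entry, "A 12-lead ECG will be taken, as described in section 7.3.12", in a block of assessments that "will be performed on the day of treatment after administration of BTG-002814". The Schedule of Visits shows ECGs at Visits 0 and 1, before and after treatment at Visit 2, and at Visits 4 and 6. Visit 3 has none.

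**Plasma.** The same Visit 2 list asks for "Blood samples for vandetanib and metabolite analysis at 2 and 4 hours after treatment, as described in section 7.3.14". Protocol 7.3.14 adds windows of 15 minutes either side of 2 h and 4 h and of 1 hour either side of 24 h, with further samples at Visits 4 and 6. No text links an ECG to any of these samples.

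**Analysis.** The SAP section 3 table for treatment day reports post-treatment QTc as the change from the pre-treatment value, by mean or median, range and standard deviation. It uses neither elapsed time nor concentration. SAP section 9 says ECGs will be summarised, without detail. SAP 4.2.1 plots concentration over time for each patient, without QTc.

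**The concern.** Protocol 8.1.8 names the hazard for oral vandetanib: T-wave change and "prolongation of the QT interval, both of which occur more commonly as the dose is increased". Protocol 3.1 says of drug-eluting beads in general that "DEB-TACE ensures slow and sustained release of the drug locally". If that carries over to this product, systemic exposure in the first minutes may be small, and an ECG taken then says little about the drug.

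This is the first human study of BTG-002814, so the treatment-day QTc change will be the first human QT evidence for it. Safety is a co-primary endpoint, and the SAP 4.1 adverse event tables have a row for QTc prolongation. Prolongation without symptoms enters that row only if an ECG is taken while exposure is present. The interim review of the first three patients (Protocol 9.6) is built on adverse events and inherits the same limit.

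The contrast with other measures is plain. Plasma has fixed times, and after treatment peak heart rate and blood pressure are to be recorded. The ECG has neither a time nor a peak rule.

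**Working it through.** The plan states no figure on this point, so there is none to reproduce. The check has three parts.

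**1. What the schedule allows**

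- Delivery: 1 mL of water plus 9 mL of contrast gives 10 mL, infused at about 1 mL per minute (Protocol 6.1.1), so about 10 minutes.
- Treatment-day ECG: any time that day after administration, so minutes after delivery is compliant.
- Next ECG: Visit 4, up to 3 days before surgery, with surgery 7 to 21 days after treatment. The earliest is 7 − 3 = day 4.
- The 24 h plasma sample falls in the gap, with no ECG beside it.

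**2. How much timing could matter (assumed model)**

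The documents give no release rate or Tmax for this product; SAP 4.2.1 lists Tmax as something the study may estimate. Assume that plasma level approaches a treatment-day plateau with half-time h and that QTc change follows concentration. The share of the plateau effect seen at time t is 1 − 2^(−t/h).

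| ECG time | h = 1 h | h = 2 h | h = 6 h |
|---|---|---|---|
| 10 min (t = 1/6 h) | 0.109 | 0.056 | 0.019 |
| 4 h | 0.938 | 0.750 | 0.370 |

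So 11% to 2% at 10 minutes, against 94% to 37% at 4 h.

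A second model lets release be much slower and includes elimination: C(t) ∝ ka/(ka − ke) × (e^(−ke·t) − e^(−ka·t)), with ka = ln 2 / release half-life and ke = ln 2 / elimination half-life. The assumed half-lives are 0.5 to 168 h for release and 48 to 480 h for elimination. Plasma level as a share of the model peak:

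| Time | Whole assumed range | Release half-life 6 h or longer |
|---|---|---|
| 15 min | about 0% to 31% | at most 4% |
| 2 h | about 1% to 96% | at most 27% |
| 4 h | about 3% to 100% | at most 48% |

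Worked case: release 6 h, elimination 48 h, so ka = 0.1155 and ke = 0.0144 per hour. At 4 h, C = 1.143 × (0.944 − 0.630) = 0.359. The peak, near 20.6 h, is 0.743. The share is 0.359/0.743 = 48%. In the slow-release cases the 24 h level is 2 to 5.6 times the 4 h level.

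**3. What pairing yields**

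ECG and plasma can be matched at four points: pre-dose, 4 h, Visit 4 and Visit 6. That is 4 × 12 = 48 pairs in 12 patients. The 12 pre-dose pairs have zero QTc change by construction, which leaves 3 × 12 = 36 post-dose pairs at most, before missing data. These are repeated measures in 12 patients, not 36 independent observations.

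The Visit 4 pairing needs one conflict settled. Protocol 7.3.14 puts that plasma sample within 24 hours before surgery, Protocol 7.2.5 puts Visit 4 up to 3 days before, and SAP 4.2.1 gives 3 days to 1 day before. As written, ECG and plasma for one visit can be days apart.

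**The case against.** The strongest reply is that the study is descriptive and unpowered, ECG sits among the other safety parameters, and no objective asks for a concentration–QTc analysis. The slow-release statement concerns drug-eluting beads in general, the dose-related QT statement concerns oral vandetanib, and the product's own swine study reported no treatment-related ECG effect. Section 7.3.12 may be meant to say how the ECG is taken rather than when. The CRF, which is not among the documents, may capture its time. All of this is fair. It limits how large the problem can be said to be, but neither the Protocol nor the SAP requires an ECG time or uses one.

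Four stronger readings are tempting and do not hold:

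- *The trial's QTc data as a whole are uninformative.* Visit 4 and Visit 6 ECGs can still show later prolongation, and SAP section 9 summarises ECGs.
- *The treatment-day change is biased towards no effect.* An unspecified time is not necessarily an early one. The dilution arises only for ECGs taken early.
- *SAP section 3 mixes treatment-day and later-visit ECGs.* Its table covers treatment day only. The mixing is across patients whose same-day ECGs may fall at different times.
- *An ECG at 4 h would capture peak effect.* If release is slow it would not, and a null result at 4 h would also be weak evidence about the peak. Matching to concentration makes that visible; an untimed ECG hides it.

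**Conclusion.** The point stands for the treatment-day QTc change. The text allows an ECG within minutes of delivery, nothing ties it to a plasma sample, and the analysis summarises it across patients without time or concentration. A null treatment-day change is therefore open to two readings, no effect or little exposure yet, and the plan gives no means of separating them.

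The size is not known from the documents. The share seen, 11% to 2% at 10 minutes against 94% to 37% at 4 h, rests on an assumed half-time of 1 to 6 h and on QTc following concentration. Over wider assumed ranges the direction is the same, but the 4 h share runs from about 3% to 100% of peak. This is a loss of first-in-human safety information that wording can largely repair; it does not invalidate the safety assessment.

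**What to change.** **Protocol and CRF**

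- Take the existing post-treatment ECG next to the 4 h plasma sample.
- Record clock times for all ECGs, and count elapsed time from the same origin as the plasma samples.
- Reconcile the Visit 4 plasma window between Protocol 7.3.14, Protocol 7.2.5 and SAP 4.2.1.
- Then take the Visit 2 pre-dose, Visit 4 and Visit 6 ECGs in the same session as that visit's plasma sample.

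**SAP section 3**

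- Report each patient's QTc change with elapsed time since administration.
- Plot QTc change against the matched vandetanib concentration, with points joined within patient and HCC or mCRC marked.
- State that 4 h may not be peak exposure, and show each patient's 4 h and 24 h concentrations beside the result.

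**Cost.** Wording changes, one plot and a small loss of scheduling freedom at site. No ECG or blood sample is added. The absence of an ECG at the 24 h sample remains, so it should be stated as a limitation.
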